We analyzed the prospectively collected data of 169 patients with ankle fracture, treated with open reduction and internal fixation (ORIF). Patients were randomized in two groups at the time of the diagnosis in the emergency department. The treatment group (T: 89 patients) were treated with a third-generation cryotherapy device (Z- One®, Zamar) which was applied daily for 2 hours two times a day up to the day of surgery. The leg was immobilized in a walking boot which was removed when the cryotherapy device was applied. The control group (C: 80 patients) did not use cryotherapy before surgery, the leg was immobilized into a half cast and elevation of the injured limb was indicated. Patients were collected in two different hospitals (Azienda Ospedaliera San Camillo Forlanini -Roma and Ospedale San Paolo – Civitavecchia) between 2021 and 2023. All patients had signed a written consent, and the study was approved by the local ethic committee.

Inclusion and exclusion criteria

Patients admitted to the emergency department with an ankle fracture were included in the current study. Exclusion criteria were open fractures, fracture-dislocations which required external fixation, patients with one or more associated fractures, and patients with a diagnose of major trauma. Patients who were not able to complain with the pre and post-surgical indications were also excluded.

Patients' assessment

A detailed physical examination was conducted in all patients, who were examined in the emergency department by local orthopedic surgeons. All patients underwent standard radiographs to diagnose the fracture, and computed tomography for the preoperative planning if indicated. After the diagnosis was made and surgical treatment was indicated, the patient was hospitalized in the department of orthopedic and trauma surgery. Patients of group T were immobilized in a walking boot to allow the use of the cryotherapy device. Patients belong to group C were immobilized in a half cast. Pain was evaluated according to the Visual Analogue Scale (VAS) and the analgesic drug demand (including morphine or acetaminophen). The Body Mass Index (BMI), number of cigarettes smoked, presence of preoperative skin complications were assessed on a daily basis.

Surgical technique

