Under loco-regional anesthesia, the patient was positioned supine with a little rise under the buttock, or in prone decubitus if posterolateral surgical approach was indicated to reduce the posterior malleolus. A tourniquet was applied at the tight, and the lower limb was prepared and draped in the usual sterile fashion. Lateral malleolus was approached first, reduced and fixed with a plate and screws. Then, surgical technique varied depending on the pattern of fracture, distal tibiofibular syndesmosis injury or associated soft tissue injury, as deltoid ligament rupture.

All patients received intraoperative antibiotic treatment, intravenous controlled analgesia for 24–48h after surgery, and standard thromboembolic prophylaxis with low molecular weight heparin (LMWE) for up to complete weight bearing. Passive motion of the ankle was encouraged from the first post-operative day.

Statistical analysis

A power analysis was performed to evaluate the sample size necessary to guarantee a power of at least 0.9 with a significance level of 0.05 using preliminary data on time to surgery.

Univariate descriptive analysis of the variables under study was carried out by calculating the centrality and variability indices for the quantitative variables and frequency tables for the variables. The homogeneity of the control group and the treatment group for the variables sex, age, type of fracture, diabetes, hypercholesterolemia, venous insufficiency, and BMI class were checked. Depending on the nature of the variables, a t-test or a chi-square test was used.

Any significant differences between the treatment and control groups were assessed using independent samples t-tests for quantitative variables and chi-square tests for qualitative variables. Where the sample size is not sufficient, the non-parametric Mann-Whitney test for independent samples was used.

An alpha significance level of 0.05 was used in all analyses mentioned. For the statistical analysis of data, IBM SPSS Statistics software version 28 was used.

CONSORT 2010 Flow Diagram

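### Seven baseline variables are only tested for homogeneity at 0.05 and enter no outcome comparison, which forgoes precision and protection against chance imbalance

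*Combined protocol and SAP*

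**What the plan says.** The Statistical analysis section describes a check of group homogeneity: "for the variables sex, age, type of fracture, diabetes, hypercholesterolemia, venous insufficiency, and BMI class were checked". The method is given next: "Depending on the nature of the variables, a t-test or a chi-square test was used". The level is the same throughout: "An alpha significance level of 0.05 was used in all analyses mentioned". The section attaches no consequence to a significant or a non-significant result.

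Outcomes are then "assessed using independent samples t-tests for quantitative variables and chi-square tests for qualitative variables". Where the sample is judged too small, "the non-parametric Mann-Whitney test for independent samples was used". No regression, analysis of covariance or stratified analysis is described.

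The sample size was set for "a power of at least 0.9 with a significance level of 0.05 using preliminary data on time to surgery". No effect size, SD or required number is given.

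The opening paragraph of the study protocol reports 169 patients (89 treated, 80 control) from two hospitals, randomised with no stratification factor mentioned. Under Patients' assessment: "The Body Mass Index (BMI), number of cigarettes smoked, presence of preoperative skin complications were assessed on a daily basis". Smoking is therefore recorded, but it is not among the seven variables checked.

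**The concern.** Under sound randomisation any baseline difference is due to chance, so a baseline p-value tests a hypothesis already known to be true. A non-significant result cannot establish that the arms are alike, because the test has little power against differences of a size that could matter. A significant result leads nowhere, because the plan does not say what would follow.

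The plan evidently regards fracture type, age and the comorbidities as worth attention, yet the outcome tests make no use of them. If some of them predict time to surgery, two things are given up. The confidence interval is wider than it needs to be. A chance imbalance in a prognostic variable also passes straight into the unadjusted difference, including one that the screen would call homogeneous.

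**Working it through.** **Inputs.** From the documents: 89 and 80 patients, alpha 0.05, power at least 0.9 on time to surgery, seven variables screened. Assumed: two-sided tests, and the share of outcome variance that the covariates explain (R²), for which the documents give nothing.

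**The plan's own figure.** The 0.9 power cannot be reproduced without an effect size and SD. Back-solving with the normal approximation:

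- SE of a difference in SD units = √(1/89 + 1/80) = 0.154.
- Difference detectable with 0.9 power = (1.960 + 1.282) × 0.154 = 0.499 SD.

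The 169 patients would thus fit a target of about 0.5 SD. This is an inference, not a stated design value.

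**What the screen lets through.**

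- Continuous variable: 1.96 × 0.154 = 0.302 SD (0.304 with the t distribution).
- Binary variable at 20%, using the common-variance approximation: 1.96 × √(0.16 × (1/89 + 1/80)) = 12.1 percentage points.
- Power to flag a true 0.2 SD difference: 25%.
- Chance of at least one flag when randomisation is sound: 1 − 0.95⁷ = 0.302, if the seven tests are independent. Correlated variables would change this figure.

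**What adjustment would gain.** With k covariate degrees of freedom, the variance of the adjusted difference relative to the unadjusted one is about VR = (1 − R²) × 166/(166 − k). Power is Φ(3.242/√VR − 1.960), where 3.242 = 1.960 + 1.282 represents the 0.9 starting point. The equivalent sample size is 169/VR.

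| R² (assumed) | VR, k = 5 | Power, k = 5 | Equivalent N, k = 5 | Power, k = 7 |
|---|---|---|---|---|
| 0 | 1.031 | 0.89 | 164 | 0.89 |
| 0.05 | 0.980 | 0.91 | 173 | 0.90 |
| 0.10 | 0.928 | 0.92 | 182 | 0.92 |
| 0.20 | 0.825 | 0.95 | 205 | 0.94 |
| 0.30 | 0.722 | 0.97 | 234 | 0.97 |

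The k = 7 column covers the example model under the fix if fracture type has three levels (an assumption): 2 for fracture type and 1 each for age, BMI, diabetes, venous insufficiency and hospital. Adjustment breaks even where R² = k/166, which is about 3% for k = 5 and 4% for k = 7.

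**What a chance imbalance does.** Suppose one covariate is out of balance by 0.25 SD. Then z = 0.25/0.154 = 1.62 and p = 0.107 by t-test, so it passes. If its correlation ρ with the outcome is 0.5 (assumed), the unadjusted difference shifts by 0.5 × 0.25 = 0.125 SD. Given the imbalance, the outcome statistic is normal with mean ρz and variance 1 − ρ². The conditional type I error is then 0.093, or 0.066 at ρ = 0.3. Averaged over all trials that pass the screen on that variable, it is 0.043 at ρ = 0.5 and 0.047 at ρ = 0.3. Over all trials it is 0.05.

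**The case against.** An unadjusted t-test, chi-square or Mann-Whitney test is a legitimate primary analysis of a randomised two-arm trial, and nothing here makes it wrong. That stands. A reader might infer from the conditional error of 0.093 that the planned comparison is anti-conservative. The documents do not support this. The figure belongs to one chosen imbalance, of a size that about 11% of randomisations would reach or exceed, in a single covariate assumed to explain 25% of the variance. The average over trials that pass the screen is slightly below 0.05.

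The size of the gain rests on assumed R² values. That also stands. At 5% the gain is about half a point to one point of power. A reader might also compute the gain from a starting power of 0.80, where 10, 20 and 30% of variance explained would raise power to 0.83, 0.87 and 0.91. The plan states at least 0.9, and the gain from there is smaller.

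It would also be too strong to call the baseline check worthless. The documents do not describe how the allocation sequence was generated or concealed, so a gross imbalance could hint at faulty allocation. It cannot certify balance. The use of BMI in classes affects only the baseline check, since no outcome analysis includes BMI.

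Finally, the document is dated 24/04/2024, patients were collected between 2021 and 2023, and the text is in the past tense. A model chosen after the outcomes were seen cannot be presented as the planned main comparison. This limits how the adjusted result may be used; it does not make the baseline p-values informative.

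**Conclusion.** The point holds as a loss of efficiency and of protection against chance imbalance, and it is worth correcting because the correction is cheap. It is not a defect of validity: overall type I error stays at 5% if randomisation was sound.

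That the seven variables are tested and then left unused is plain from the text. The benefit of using them is uncertain. With 5 degrees of freedom it runs from a loss of about one point of power if they explain nothing to a gain of about seven points if they explain 30% of the variance in time to surgery. This rests on a two-sided 0.05 test, a true starting power of 0.9 and a roughly linear covariate effect.

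**What to change.** 1. Drop the baseline t-tests and chi-square tests. Show a descriptive table by arm with standardised differences, and add smoking at entry.
2. Add a linear model for time to surgery with arm plus a small fixed set of entry covariates, chosen on prognostic grounds and kept whatever the observed balance. An example set is fracture type, age, continuous BMI, diabetes, venous insufficiency and hospital. Report the adjusted difference with its 95% CI.
3. Report the planned t-test or Mann-Whitney test beside it, and check the model for skewness of time to surgery.
4. Use only the first recorded BMI and smoking values, because later daily values follow randomisation.
5. Limit any adjusted model for skin complications to one or two covariates, because the number of events is not given.
6. If outcomes have already been analysed, label the adjusted result post hoc and supplementary, and do not make it the main comparison.

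The cost is a few lines of SAP text and one further model in the software already named, with no new data provided that hospital and entry values are held in the dataset. The statistical downside, if the covariates explain nothing, is about 3% in variance with 5 degrees of freedom or 4% with 7 (power 0.90 to about 0.89).

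### Time to surgery is compared without hospital, although patients came from two hospitals; the test stays valid, but precision may be lost, by an unknown and possibly small amount.

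*Combined protocol and SAP*

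**What the plan says.** The opening paragraph of the study protocol states that "Patients were collected in two different hospitals" and that "Patients were randomized in two groups at the time of the diagnosis in the emergency department". It gives arm sizes only overall: 89 treated and 80 control, 169 in all. It does not state an allocation ratio or any stratification by hospital. The flow diagram is not shown in the supplied text, so it may hold more.

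Time to surgery is the first effect named in the aim. It is also the outcome behind the power analysis, which targets "a power of at least 0.9 with a significance level of 0.05 using preliminary data on time to surgery".

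The Statistical analysis section gives one rule for comparing the arms: "Any significant differences between the treatment and control groups were assessed using independent samples t-tests for quantitative variables and chi-square tests for qualitative variables". It adds: "Where the sample size is not sufficient, the non-parametric Mann-Whitney test for independent samples was used". Homogeneity of the groups "for the variables sex, age, type of fracture, diabetes, hypercholesterolemia, venous insufficiency, and BMI class were checked"; hospital is not in that list. No regression, stratified test or hospital term appears anywhere.

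**The concern.** After admission, the wait for an operation may depend on how each hospital organises its work as well as on the state of the ankle. Hospital is therefore a natural baseline factor for this outcome. It is known for every patient and uses one degree of freedom. If waits differ between the hospitals, that difference stays in the error term of an unadjusted test. The standard error, and any confidence interval built on it, is then larger than necessary.

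A second point concerns what the reader can verify. The unadjusted comparison is unbiased if the allocation ratio was the same at both hospitals. With arm sizes given only in total, that condition cannot be checked.

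**Working it through.** **Inputs from the document.** Arms of 89 and 80; significance level 0.05; power at least 0.9; two hospitals.

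**Inputs assumed.** Two-sided testing; share *p* of patients in one hospital, from 50:50 to 90:10; gap *g* between hospital mean waits, in within-hospital SDs.

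**The plan's own figure.** The stated power cannot be reproduced, because no effect size, SD or required sample size is given. Solving backwards with the noncentral t distribution (167 df, SE factor √(1/89 + 1/80) = 0.154), 90% power corresponds to a difference of 0.502 total SD. That serves as the reference effect.

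**Precision lost.** The ratio of unadjusted to hospital-adjusted variance is V = 1 + p(1−p)g². Then:

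- share of variance explained by hospital = 1 − 1/V;
- excess standard error (and CI width) = √V − 1;
- adjusted power = power at 0.502·√V with 166 df.

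For example, at 50:50 and g = 0.5: V = 1 + 0.25 × 0.25 = 1.0625; explained share 5.9%; √V − 1 = 3.1%; power 91.6%.

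| Split | g | V | Excess SE | Adjusted power |
|---|---|---|---|---|
| 50:50 | 0.25 | 1.016 | 0.8% | 90.4% |
| 50:50 | 0.5 | 1.063 | 3.1% | 91.6% |
| 50:50 | 1.0 | 1.250 | 11.8% | 95.2% |
| 80:20 | 0.25 | 1.010 | 0.5% | 90.3% |
| 80:20 | 0.5 | 1.040 | 2.0% | 91.1% |
| 80:20 | 1.0 | 1.160 | 7.7% | 93.7% |
| 90:10 | 0.25 | 1.006 | 0.3% | 90.2% |
| 90:10 | 0.5 | 1.023 | 1.1% | 90.6% |
| 90:10 | 1.0 | 1.090 | 4.4% | 92.3% |

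**Cost of estimating the hospital term.** Under simple randomisation the adjusted variance grows by about 1 + 1/(169 − 4) = 1.006. Adjusted power over the table then runs from 90.0% to 95.1%. With no gap at all it is 89.8%, so adjustment costs about 0.2 percentage points.

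**Chance imbalance is the same loss.** At 50:50 the arms' hospital shares differ by chance with an SD of √(0.25 × (1/89 + 1/80)) = 7.7 percentage points. With g = 1 that shifts the estimate by 0.077 SD, whose square is 0.0059. The extra variance in the unadjusted estimate is p(1−p)g²(1/89 + 1/80) = 0.25 × 0.02374 = 0.0059. The two are equal, so imbalance must not be counted again.

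**False-positive rate.** This was simulated with 20,000 trials per setting, at (split, gap) of (50:50, 1.0), (50:50, 0.5), (80:20, 1.0) and (90:10, 0.25).

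| Randomisation | Unadjusted t-test | With hospital term |
|---|---|---|
| Simple | 0.048 to 0.052 | 0.048 to 0.052 |
| Stratified by hospital | 0.028 to 0.048 | 0.049 to 0.050 |

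**Skewed waits.** With lognormal waits (6,000 trials per setting), Mann-Whitney power was 0.902 and hospital-stratified rank-test power 0.944 at (50:50, 1.0). At (90:10, 0.25) they were 0.890 and 0.889. The pattern is the same.

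**If the allocation ratio had differed by hospital.** This is illustration only; nothing in the documents suggests it. Take equal hospitals with treatment probabilities 0.60 and 0.45. The first hospital's share is 0.60/1.05 = 0.571 of the treated and 0.40/0.95 = 0.421 of the controls, a difference of 0.150. The unadjusted estimate is then biased by 0.150·g. For g = 0.5 that is 0.075 against an SE of about 0.154 × √1.0625 = 0.159, and the false-positive rate is about 0.08. For g = 1.0 it is 0.150 against about 0.172, and the rate is about 0.14.

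**The case against.** The best reply is that nothing here is invalid. Under sound randomisation the unadjusted t-test keeps its error rate, and under stratification it is conservative. Every figure for the loss depends on a split and a gap that the documents do not give. The 12% figure needs equal hospitals and a full-SD gap together. If the hospitals barely differ, adjustment gains nothing. The 90% baseline is itself back-solved: at an assumed effect of 0.6 SD, unadjusted power is already 97.2%, and adjustment at (50:50, 0.5) brings it only to 97.9%. The plan describes tests rather than intervals, and its data have already been analysed, so power is of limited use now. A baseline test on hospital would not change the analysis either.

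Most of this stands, and it limits how strongly the point should be pressed. The modest range deserves first place, and the omission from the balance check matters little in itself. What it does not answer is that a hospital term is a better method at almost no cost (about 0.2 points of power at worst in these calculations). Nor does it supply the counts needed to confirm equal allocation. Absence of results tables from the supplied text is no fault in the plan, but the planned analyses do not describe such a table.

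**Conclusion.** The concern holds as a matter of precision, not validity. Hospital is absent from every comparison of time to surgery and from the balance list. Assuming sound randomisation with one allocation ratio, two-sided 0.05 and 90% unadjusted power at 89 versus 80, the unadjusted standard error is 0.3% to 3% too large for gaps of 0.25 to 0.5 SD. It is up to about 12% too large for a gap of 1.0 SD with equal hospitals. Adjusted power is 90.2% to 91.6% in the first range and reaches 95.2% at the extreme, before the small estimation cost. The true size cannot be found from the documents and may be negligible. The change should be made, but the original test does not need rescuing unless the counts by hospital reveal unequal allocation.

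**What to change.** 1. Report patient numbers and time to surgery by hospital and arm, and state the allocation ratio and whether randomisation was stratified by hospital.
2. Fit one linear model for time to surgery with treatment and hospital only, and give the adjusted mean difference with a 95% CI.
3. If waits are clearly skewed, judged on pooled data without arm labels, use a hospital-stratified rank test instead. It answers a rank question rather than one about means, so say which was used and why.
4. Show the result beside the original unadjusted test and label it as added after the original analysis.
5. Add fracture type, age or BMI class only as a labelled sensitivity analysis with values from admission, since the Patients' assessment section describes BMI as recorded daily.

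The cost is low: one table and one two-term model in SPSS 28, which the plan already uses, on data already held, with no further patients. A stratified rank test may need a short extra step. The drawback is that the adjusted result is not pre-specified, and viewing pooled data gives only limited protection once the arms have been compared. That is why it should accompany the original test and not replace it.

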Title of the study: Third generation cryotherapy reduces time to surgery and local complication in patients with ankle fractures: a prospective randomized controlled trial.

Type of the Paper: Randomized Controlled Trial.

NCT number: not available

Article ID: cryotherapy012021.n01

Date of the document: 24/04/2024

This is a RCT about the preoperative use of third generation cryotherapy in patients hospitalized for ankle fracture. The aim of this study is to assess the effects of third generation cryotherapy on time to surgery, pain, opioids intake, and local skin complications. Although the use of cryotherapy is traditionally believed to reduce pain, swelling, local skin complications and the need of analgesia, the results on ankle surgery are not well reported and still contradictory. The working hypothesis is that third generation cryotherapy is a safe, reduces time to surgery and is useful in the surgical management of ankle fractures

We confirm that each author of this article meets the journal's criteria for authorship. We confirm that the manuscript has not been submitted or is not simultaneously being submitted elsewhere, and that no portion of the data has been or will be published in proceedings or transactions of meetings or symposium volumes.

Fiximed Italia, Rome, Italy, funded the APC, but the company had no role in the design of the study, in the collection, analyses, or interpretation of data, in the writing of the manuscript, and or in the decision to publish the results.

The authors declare no external funding or other benefits from commercial sources for the work reported on in the manuscript, nor any other financial interests which could create a potential conflict of interest.

Thank you

Kind regards

Third generation cryotherapy reduces time to surgery and local complication in patients with ankle fractures: a prospective randomized controlled trial.

Study protocol and statistical analysis

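### No primary outcome is declared, and the title's claim of reduced local complication rests on an undefined measure tested at an unadjusted 0.05

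*Combined protocol and SAP*

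**What the plan says.** - **Aim (cover page):** the study is to "assess the effects of third generation cryotherapy on time to surgery, pain, opioids intake, and local skin complications". The four outcomes are not ranked, and none is called primary or secondary anywhere in the document.
- **Working hypothesis (cover page):** "third generation cryotherapy is a safe, reduces time to surgery and is useful in the surgical management of ankle fractures". Time to surgery is the only specific reduction named.
- **Title:** "Third generation cryotherapy reduces time to surgery and local complication in patients with ankle fractures". Two effects are claimed.
- **Sizing (Statistical analysis):** "a power of at least 0.9 with a significance level of 0.05 using preliminary data on time to surgery". No other outcome is mentioned there.
- **Tests (Statistical analysis):** "Any significant differences between the treatment and control groups were assessed using independent samples t-tests for quantitative variables", with chi-square for qualitative variables and Mann-Whitney where the sample is too small. No threshold for that switch is given.
- **Significance level (Statistical analysis):** "An alpha significance level of 0.05 was used in all analyses mentioned".
- **Measurement (Patients' assessment):** "Pain was evaluated according to the Visual Analogue Scale (VAS) and the analgesic drug demand (including morphine or acetaminophen"; and "presence of preoperative skin complications were assessed on a daily basis". No per-patient summary or time point follows for pain, opioid intake or skin complications.

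**The concern.** A headline claim should rest either on the primary outcome or on a secondary outcome protected by a stated rule. Here the title places local complication beside time to surgery as an established effect. The trial was not sized on it, no rule protects it, and its per-patient definition is missing. Daily assessment could yield any event before surgery, the number of days affected or the number of events. These are different variables, and choosing among them after seeing the data would add to the error rate.

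The document cannot settle what was fixed in advance. It is dated 24/04/2024, patients were collected between 2021 and 2023, the analysis is described in the past tense, and the title already states the result. A reader therefore cannot tell whether the complication claim is confirmatory or one of several unadjusted looks.

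**Working it through.** **The plan's own figure.** The stated power of at least 0.9 for time to surgery cannot be reproduced, because no effect size, standard deviation, sidedness or planned sample size is given. It is used here only to show which outcome the sizing rests on.

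**Inputs from the document.** Four outcomes in the aim; 0.05 for every analysis; 89 treated and 80 control patients analysed.

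**Assumptions.** Two-sided tests; one test per outcome; no true effect on the outcomes counted; jointly normal test statistics with a common correlation rho of 0 to 0.7. The document gives no correlations.

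**Step 1. One test.** A two-sided 0.05 test gives a false result in favour of cryotherapy with probability 0.05 / 2 = 0.025.

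**Step 2. Three outcomes other than time to surgery.** This is the relevant count if time to surgery was designated beforehand. With rho = 0:

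- at least one false benefit: 1 − 0.975³ = 0.073
- at least one false difference in either direction: 1 − 0.95³ = 0.143

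With rho > 0, write each statistic as √rho·U + √(1 − rho)·E and integrate over U. For false benefit, the probability is 1 − ∫ φ(u)·Φ((1.960 − √rho·u)/√(1 − rho))³ du.

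| rho | 0 | 0.3 | 0.5 | 0.7 |
|---|---|---|---|---|
| At least one false benefit | 7.3% | 6.8% | 6.3% | 5.5% |
| At least one false difference | 14.3% | 13.6% | 12.5% | 10.9% |

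**Step 3. Sensitivity to the count.** If analgesic demand is taken as part of pain, two outcomes remain. False benefit is then 1 − 0.975² = 4.9% at rho = 0, falling to 4.2% at rho = 0.7.

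**Step 4. If nothing was designated beforehand.** All four outcomes count. False benefit is 1 − 0.975⁴ = 9.6%, falling to 6.5%. Any false difference is 1 − 0.95⁴ = 18.5%, falling to 13.0%.

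**Step 5. Cost of adjustment for skin complications.** Holm's strictest step across three outcomes is 0.05 / 3 = 0.0167. Two-proportion power (pooled normal approximation, 80 control and 89 treated), with all rates assumed because none is given:

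| Control vs treated | at 0.05 | at 0.0167 |
|---|---|---|
| 10% vs 5% | 24% | 13% |
| 20% vs 10% | 45% | 29% |
| 30% vs 10% | 91% | 81% |

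**The case against.** The strongest reply is that the primary outcome is plain in substance. Time to surgery alone sized the trial, comes first in the title and the aim, and is the only specific reduction hypothesised. An earlier plan, perhaps the one submitted to the ethics committee, may declare it. This largely stands. What is shown is that this document does not declare a primary outcome, not that none was ever designated. A reader might infer that the 5% level for time to surgery is lost, or that 18.5% is the trial's error rate. The document does not support that unless there was no prior designation.

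A reader might also infer that no test is specified for skin complications. That goes too far: tests are assigned by variable type, and a yes/no presence variable would go to chi-square. What is missing is the measure and its time point, which decide what type of variable it is.

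It is also fair to say that skin complications are a stated outcome in the aim, and that the words on safety and usefulness in the hypothesis may cover them. Their absence by name therefore carries little weight. Being listed in the aim, however, gives an outcome neither a definition nor error control.

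Finally, the inflation is modest, and the title makes only one claim beyond time to surgery. That is correct, and it limits the severity. It does not make the claim confirmatory.

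**Conclusion.** The point holds as a reporting and error-control gap that should be closed. If time to surgery was designated beforehand, its 5% level stands. The other three outcomes together then carry a chance of at least one false benefit of about 5.5% to 7.3%, against 2.5% for one test, under the assumptions listed. The local-complication claim in the title falls in that unprotected group and has no per-patient definition.

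Two further inferences are not supported. The document does not show that the complication finding is false: it gives no p-values or event rates, so whether any claim would change is unknown. Nor does it show that power for this outcome was low. Power is undocumented, and over the assumed rates above it runs from 24% to 91%. Confidence is medium, because an earlier document could resolve the question of designation.

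**What to change.** 1. Name time to surgery as the single primary outcome at two-sided 0.05. Cite the earlier dated document that designated it, or label the choice post hoc.
2. Define one per-patient skin-complication measure (for example, any skin complication before surgery, yes or no), and one measure and time point each for pain and opioid intake.
3. Allow confirmatory claims on these three, by Holm and only after a significant result on time to surgery, if both the designation of time to surgery and the measures are shown to have been fixed before the data were seen. Holm applied to measures chosen now from the daily records would not restore error control.
4. Otherwise report the three as exploratory with 95% confidence intervals, and remove local complication from the title's claim of effect.

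**Cost.** No new data are needed, though the measures may have to be re-derived from the daily records. Time to surgery loses no power if it was designated beforehand. Secondary claims face stricter thresholds under Holm, with skin-complication power reduced as in the last table. The exploratory route costs no power but gives up the confirmatory complication claim.
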